### **7.6.4 Post-Implant**

Post-implant imaging will be used to confirm any occurrence(s) of worsening of TR severity, tricuspid valve and leaflet condition, and any evidence of device embolization, Single Leaflet Device Attachment (SLDA), bleeding, perforation, etc. Treatments for these will be per physicians' discretion. Final TTE and TEE echocardiograms may be acquired and saved by the site.

Immediately following the TriClip™ procedure, heparin (or alternative anticoagulation therapy, e.g., bivalirudin) should be discontinued and the ACT should be monitored in accordance with hospital protocols. Vascular sheaths should be removed according to usual hospital practice.

Post- TriClip™ procedure anticoagulation is recommended per the Investigator's discretion or as described in Section 7.7.3.

### **7.7 Post-procedure (Roll-in, Device Group and Single-arm Cohort; In-hospital)**

Subjects will receive standard post-cardiac catheterization procedure care as judged appropriate by the Investigator. Subjects should be advised to limit strenuous physical activity for the first month following the TriClip™ procedure or longer, as deemed appropriate by the Investigator.

The medication recommendations below are reflective of the device arm only. For the Control group, subjects should be optimized on medical management prior to enrollment. Frequent changes to medications in the control group should be avoided and only performed if clinically indicated.

### **7.8 Discharge (Roll-in, Device Group and Single-arm Cohort)**

Prior to discharge (Discharge occurs when subject leaves the implanting hospital), the following required tests and procedures should be completed (> 16 hours post TriClip™ procedure and no later than day of discharge) as outlined below, and the information should be captured on the appropriate eCRFs:

- 12-lead ECG
- Blood draw
- Concomitant cardiovascular medication logs

## TRILUMINATE Pivotal CIP (Version F)

- Physical exam including vital signs (weight, heart rate and blood pressure)
- Echocardiogram (TTE)
- Adverse events
- Protocol deviations
- Device deficiency
- NYHA Functional Class assessment

Each subject implanted with a Clip(s) must be provided the Implant Identification Card, included in each TriClip™ System package. The subject must be instructed to keep this Implant Identification Card on their person at all times. The serial number of all implanted TriClip™ (s) must be recorded on the Implant Identification Card.

### 7.8.1 Post-Procedure Medications

#### 7.8.1.1 Antibiotic Therapy

Administer additional intravenous doses of antibiotics at approximately 6 and 12 hours (or per institutional guidelines) after the completion of the procedure.

The Investigator should instruct all subjects who receive the TriClip™ device of the need for endocarditis prophylaxis, as recommended in the ACC/AHA 2008 Guideline Update on Valvular Heart Disease: Focused Update on Infective Endocarditis. Subjects should be instructed to notify the Investigator or the subject's primary care physician in the event that a procedure recommended by this Guideline is planned, so that prophylactic antibiotics can be prescribed. A prescription for endocarditis prophylaxis may be provided to the subject at discharge.

#### 7.8.1.2 Antiplatelet/Anticoagulation Therapy

Following placement of the TriClip™ device, anticoagulation therapy is prescribed. If a loading dose of clopidogrel was not given prior to the TriClip™ procedure, it may be administered after the procedure at investigator discretion. Post- TriClip™ procedure anticoagulation is as follows:

1. Reinitiate warfarin, dabigatran or factor Xa inhibitor (if discontinued for the TriClip™ procedure) at pre-procedure levels or as appropriate. If chronic oral anticoagulation is used, aspirin and clopidogrel use are not recommended, but are allowed if otherwise indicated for other conditions.
2. If chronic oral anticoagulation is not used, it is strongly recommended that either daily clopidogrel (75 mg) and/or aspirin ( $\geq 75$  mg) is administered for 6 months or longer. If aspirin is to be used, a loading dose of 325 mg acetylsalicylic acid (ASA) may be administered either pre- or immediately post- TriClip™ procedure followed by  $\geq 75$  mg per day for 6 months or longer at the Investigator's discretion.

#### 7.8.1.3 Management of Hypertension

Subjects should have their blood pressure checked prior to discharge. Subjects should be prescribed medication as necessary following current standard of care to maintain normotensive blood pressure.

#### 7.8.1.4 Cardiovascular Medications

Subjects must continue to take baseline medications without change during follow-up, unless clinically (medically) necessary. If there are any cardiovascular medication changes (including

Study Document No: ABT-CIP-10249

Study Name: TRILUMINATE Pivotal

**CONFIDENTIAL:** May not be reproduced outside of Abbott without written permission from Document Control. This is a quality record which will be retained per the local retention policy.

**TRILUMINATE Pivotal CIP**  
(Version F)

dosage changes), these changes, and the reason for change must be documented on the electronic case report form.

## **7.9 “Treatment” Visit (Control Group)**

The “Treatment” visit in the Control group must occur between 0 and 14 days after randomization. At the “Treatment” visit, Control group subjects will be seen by the HF specialist investigator, and will undergo a physical exam, including vital signs, cardiac health status and evaluation of heart failure medications.

## **7.10 Follow-up Assessments**

### **7.10.1 Follow-up CIP Medications**

Subjects must continue to take baseline medications without change during follow-up, unless clinically (medically) necessary. If there are any cardiovascular medication changes (including dosage changes), these changes, and the reason for change must be documented on the electronic case report form.

Subjects should have their blood pressure checked. Subjects should be prescribed medication as necessary following current standard of care to maintain normotensive blood pressure.

### **7.10.2 Follow-up for All Subjects**

Required clinical follow-up will be performed at the following intervals (based on treatment visit) for all subjects with TriClip™ procedure attempt, regardless of whether a TriClip™ was successfully implanted:

- Discharge post-TriClip™ procedure
- 30 days (-3/+14 days) follow-up visit (this visit must be conducted even if subject is in hospital)
- 6 months (180 days ± 28 days) follow up visit
- 1 year (365 days ± 28 days) follow up visit
- 18 months (545 days ± 28 days) follow up visit
- 2 years (730 days ± 28 days) follow up visit
- 3 years (1095 days ± 28 days) follow up visit
- 4 years (1460 days ± 28 days) follow up visit
- 5 years (1825 days ± 28 days) follow up visit

Follow-up visits will be calculated from the date of the Index Procedure (for subjects receiving the device) and the Treatment visit for subjects in the Control group. Follow-up assessments can be performed at any point in the window, and should be conducted, whenever possible, by the same individual who performed the baseline tests. The subject should be followed at the investigational site where the subject was enrolled and may be followed at another investigational site only with prior agreement from that site’s Investigator and from the Sponsor.

At the 30-day follow-up visit, the echocardiographer shall examine the integrity of the TriClip™. Subjects must continue to take baseline medications without change during follow-up, unless clinically (medically) necessary. If there are any cardiovascular medication changes (including dosage changes), these changes should be documented on the electronic case report form. In general, neurohormonal antagonists should not be changed. Subjects implanted with the

Study Document No: ABT-CIP-10249

Study Name: TRILUMINATE Pivotal

**CONFIDENTIAL:** May not be reproduced outside of Abbott without written permission from Document Control. This is a quality record which will be retained per the local retention policy.

## TRILUMINATE Pivotal CIP (Version F)

TriClip™ must also be evaluated for device integrity. Required tests and procedures outlined below must be completed. Timing of specific tests will follow the Clinical Evaluation Schedule (**Table 1**) outlined below. These clinical assessments are standard assessments for most cardiac/structural heart interventional procedures and therefore should be administered per standard of care at each Institution. All visits and tests must be completed even if the subject is in hospital. Refer to the Schedule of Events table section 7.15 for timing of below listed tests.

- 12-lead ECG
- Blood draw
- Physical exam including vital signs (weight, heart rate and blood pressure)
- Echocardiogram – TTE at all follow-up visits
- Modified Rankin Scale (Required at visits occurring after onset of stroke)
- 6-Minute Walk Test (6MWT)– See **APPENDIX XIII** for 6 Minute Walk Test Guidelines
- Concomitant cardiovascular medications assessment
- NYHA Functional Class assessment
- KCCQ QoL and SF-36 questionnaires to be completed by the subject – must be administered by “blinded” study personnel. Note: To minimize bias and undue influence, the QoL questionnaires will be completed by the subject, unless the subject is unable to complete the questionnaire on their own (a note to file must be completed to document the inability of subject to complete the questionnaire)
- Assess and record adverse events
- Assess and record protocol deviations

All subjects should continue to be monitored and treated per applicable standards of care consistent with the subject’s condition. The site Principal Investigator should collaborate with the other site investigators as applicable in determining the treatment strategy for all subjects enrolled at their site. The electronic case report forms will document changes in treatment strategy (i.e. new use of CRT, PCI, tricuspid valve surgery, and/or mitral valve surgery) and who was involved with determining changes in treatment strategy. Subjects implanted with the Clip must be evaluated for device integrity.

### **7.11 TriClip™ Intervention in Control Group Subjects or Additional TriClip™ Intervention in Roll-in, Device Group or Single-arm Cohort Subjects**

Control group subjects will not be allowed to undergo the TriClip™ procedure until after completion of the 12-month visit. TriClip™ intervention in the Control group prior to the 12-month visit will be considered a major protocol deviation. Prior to TriClip™ procedure attempt in, a Control group subject upon completion of 12-month visit, the subject must be rescreened and evaluated by the ECL and EC to assess eligibility. A 30-Day Post-TriClip™ Follow-up visit must be completed 30 days (-3/+14 days) after the TriClip™ procedure. This visit should still be completed even if the subject is in hospital. The same assessments shall be performed as done for the 30-day follow-up. Following the 30-day post procedure visit the patient will continue with their predetermined visit schedule.

It may be necessary for a roll-in, Device group, single-arm, or cross-over subject to undergo additional TriClip™ procedures. A TTE must be performed within 90 days prior to a TriClip™ procedure in either group. A 30-day Post- TriClip™ Follow-up visit must be completed 30 days (-3/+14 days) after the additional TriClip™ procedure. This visit should still be completed even if

Study Document No: ABT-CIP-10249

Study Name: TRILUMINATE Pivotal

**CONFIDENTIAL:** May not be reproduced outside of Abbott without written permission from Document Control. This is a quality record which will be retained per the local retention policy.

**TRILUMINATE Pivotal CIP**  
(Version F)

the subject is in hospital. The same assessments shall be performed as done for the 30-day follow-up. If this visit window overlaps with another study follow-up visit window, only one study visit is needed to satisfy these requirements.

## **7.12 Tricuspid Valve Surgery**

For inclusion into this trial, all subjects prior to enrollment are expected to be at intermediate or greater risk for mortality or morbidity post tricuspid valve surgery. If a subject's condition worsens considerably due to TR (regardless of study arm or group assignment), then the subject can undergo tricuspid valve surgery provided that both the heart failure specialist and the surgeon deem that tricuspid valve surgery is required. The sponsor will be notified of this occurrence. A TTE must be performed within 90 days prior to tricuspid valve surgery and provided to the ECL for assessment.

A 30-Day Post-Tricuspid Valve Surgery Follow-up visit must be completed 30 days (-3/+14 days) after the tricuspid valve surgery. This visit should still be completed even if the subject is in hospital. If this visit window overlaps with another study follow-up visit window, only one study visit is needed to satisfy these requirements. Subjects will continue to be followed per this Clinical Investigational Plan.

### **7.12.1 30-Day Post-Tricuspid Valve Surgery Follow-up**

Requirements for the 30-day Post-Tricuspid Valve Surgery Follow-up visit are described below.

- 12-lead ECG
- Blood draw
- Physical exam including vital signs (weight, heart rate and blood pressure)
- Echocardiogram (TTE)
- Modified Rankin Scale (Assessment of mRS should be performed only after onset of stroke, if stroke occurred)
- Concomitant cardiovascular medications assessment
- NYHA Functional Class assessment
- Assess and record adverse events
- Assess and record protocol deviations

## **7.13 Explanted TriClip™ Device**

The TriClip™ device may be explanted during tricuspid valve surgery or an autopsy. If possible, fluoroscopic images with side views of the device should be obtained prior to explant. Following explant of the TriClip™ device(s) during surgery, the subject will continue follow-up schedule based on index procedure date. Explant information will be captured on the Tricuspid Valve Surgery Form or Death Form.

## **7.14 Patient Reported Outcome (PRO) Measures**

The Kansas City Cardiomyopathy Questionnaire (KCCQ) is a 23-item self-administered questionnaire/PRO developed to independently measure the patient's perception of their health

Study Document No: ABT-CIP-10249

Study Name: TRILUMINATE Pivotal

**CONFIDENTIAL:** May not be reproduced outside of Abbott without written permission from Document Control. This is a quality record which will be retained per the local retention policy.

**TRILUMINATE Pivotal CIP**  
(Version F)

status, which includes heart failure symptoms, impact on physical and social function, and how their heart failure impacts their quality of life (QOL) within a 2-week recall period.

The SF-36 is a 36 item scale constructed to survey health status and quality of life. The form asks participants to reply to questions according to how they have felt in the previous week. The SF-36 can be summarized into two summary scores representing physical and mental components of health and can also be used to derive health related quality of life index values.

A blinded coordinator or designee will administer KCCQ and SF-36 questionnaires during the follow up visits (30-day visit and afterwards). KCCQ and SF-36 questionnaires must be completed by the subject. It is important the subject understands the meaning of all words and instructions in the questionnaires. The subject should be instructed to ask any questions about the questionnaires if further explanation is needed. Once the questionnaires are completed, the Coordinator or designee will review for completeness to verify that all questions have been answered according to the directions provided.

To minimize bias and undue influence, the KCCQ and SF-36 questionnaires will be completed by the subject, unless the subject is unable to complete the questionnaires on their own (in such cases a note to file must be completed to document the inability of subject to complete the questionnaire).

**TRILUMINATE Pivotal CIP**  
(Version F)

**7.15 Schedule of Events**

**Table 1: Clinical Evaluation Schedule**

CIP Activity	Screening	Baseline	Procedure	Discharge (>16hr post-procedure)	30 days (-3/+14 days)	6 Month (±28 days)	12, 18 months, 2-5 years (±28 days)
Informed Consent Process	X						
Demographics	X						
Physical Examination & Vital Signs	X	X	X b	X	X	X	X
Local Heart Team Evaluation	X						
Cardiovascular History	X						
Medical History	X						
Cardiovascular Medications	X	X	X	X	X	X	X
Echocardiogram	X (TTE and TEE)	X (TTE only) a	X (TEE only)	X (TTE Only)	X (TTE only)	X (TTE Only)	X e (TTE only)
RHC	X						
CT c		X c			X c		X c (1 year only)
MRI		X c			X c		
CBC with differentials and platelet count	X	X a		X	X	X	X
Gamma-GGT d , BNP or NT-proBNP, CK or CK-MB, BUN, serum creatinine, AST, ALT, INR (while on anticoagulation), Bilirubin, Serum Sodium	X	X a		X	X	X	X
KCCQ		X			X g	X g	X e, g
SF-36		X			X g		X (1 and 2 year only) g
6-Minute Walk		X				X g	X e, g
NYHA FC	X	X		X	X g	X g	X g
12-lead ECG	X	X	X b	X	X	X	X
Modified Rankin Scale f				X	X	X	X
Hospitalizations	X (prior 12 months)	X	X	X	X	X	X
Adverse Events/Deviation		X	X	X	X	X	X
Device Deficiency			X	X	X	X	X
Withdrawal		X	X	X	X	X	X

a If performed within 14 days of assessment for screening, then screening can be used for baseline.

b Must be performed within 24 hours prior to procedure (Device, Single-arm and Roll-in Group).

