#### Peri-procedural MI ( $\leq 72$ hours after TriClip™ procedure)

Mandatory: CK-MB (preferred)  $\geq 10x$  ULN within 72 hrs. post- TriClip™ procedure in patient with normal baseline CK-MB

OR

Mandatory: CK-MB  $\geq 5x$  ULN within 72 hrs. post- TriClip™ procedure in patient with normal baseline CK-MB *plus* new pathological Q-waves in  $\geq 2$  contiguous leads, or new LBBB

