#### Post-surgery

Mandatory: CK-MB  $\geq 10x$  ULN (preferred) within 24 hrs. of cardiothoracic surgery *plus 1 of the following*:

- New pathological Q-waves in  $\geq 2$  contiguous leads or new persistent LBBB on ECG  $\geq 30$  min. and  $\leq 72$  hrs. post-CABG cardiothoracic surgery, or

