**Spontaneous MI (>72 hours after TriClip™ procedure)**

Any one of the following criteria:

- Detection of rise and/or fall of cardiac biomarkers (CK-MB) with at least one value above the upper limits of normal (ULN), together with evidence of myocardial ischemia with at least one of the following:
  - ECG changes indicative of new ischemia [new ST-T changes or new left bundle branch block (LBBB)]
  - New pathological Q waves in at least two contiguous leads
  - Imaging evidence of new loss of viable myocardium or new wall motion abnormality
- Sudden, unexpected cardiac death, involving cardiac arrest, often with symptoms suggestive of myocardial ischemia, and accompanied by presumably new ST elevation, or new LBBB, and/or evidence of fresh thrombus by coronary angiography and/or at autopsy, but death occurring before blood samples could be obtained, or at a time before the appearance of cardiac biomarkers in the blood.
- Pathological findings of an acute myocardial infarction.

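### Table 1 accepts total CK in place of CK-MB, but both routes to a peri-procedural MI need CK-MB at baseline and after the procedure

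*Protocol*

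**What the plan says.** Protocol section 7.15, Table 1, has one row for blood chemistry. It includes "CK or CK-MB, BUN, serum creatinine" and is marked at screening, baseline, discharge, 30 days and every later visit, but not in the procedure column. No footnote narrows the choice between the two enzymes. The footnote about site capability attaches to gamma-GGT alone. Another footnote lets screening bloods serve as baseline if taken within 14 days.

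The sections that describe the visits (6.2.1, 7.3.1, 7.8 and 7.10.2) ask for a blood test or blood draw without naming CK-MB.

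Appendix II, under Myocardial Infarction, defines a peri-procedural MI by either of two routes:

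- Route 1 opens "Mandatory: CK-MB (preferred" and asks for at least 10 times ULN within 72 hours, "in patient with normal baseline CK-MB".
- Route 2 asks for at least 5 times ULN within 72 hours, "in patient with normal baseline CK-MB *plus* new pathological Q-waves in" two or more contiguous leads, or new LBBB.

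Section 11.9.4 has the CEC adjudicate prespecified events by the definitions in the Protocol. SAP section 3.2 summarises CEC-adjudicated adverse events by treatment group, as event counts and as the percentage of subjects with events among all enrolled.

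**The concern.** The schedule decides which assay is on file, and the definition decides what an adjudicator may call an MI. Here the two do not match. A site can follow Table 1 to the letter and still not hold the values that Appendix II demands.

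The missing baseline is the harder part. A suspected event can prompt a CK-MB after the procedure, but a CK-MB from before the procedure cannot be obtained afterwards. An event that shows only as an enzyme rise might not prompt any extra test.

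What is at stake is the completeness of one safety event. Peri-procedural MI can arise only in people who undergo the procedure, so any loss understates a risk of the procedure. The extent of the loss would follow each site's choice of assay. Safety is part of the trial objective, and the earlier single-arm TriClip trial recorded one MI through six months (Protocol section 2.1.4, which does not give its timing relative to the procedure).

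**Working it through.** The plan states no figure on this point and none can be derived, so the check is a comparison of text.

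1. **Baseline.** Both peri-procedural routes (2 of 2) require a normal baseline CK-MB. Table 1 secures either CK or CK-MB at baseline. At a CK-only site the condition cannot be shown to be met.

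2. **After the procedure.** Both routes require CK-MB within 72 hours. Table 1 has no chemistry at the procedure visit, so the discharge draw is the only scheduled candidate. Section 7.8 places it more than 16 hours after the procedure and no later than the day of discharge. That gives two gaps: the enzyme may be CK, and nothing keeps the draw inside 72 hours if the stay exceeds 72 / 24 = 3 days. The next scheduled draw belongs to the 30-day visit, whose window opens at day 30 − 3 = 27.

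3. **Substitute thresholds.** The MI definitions give no total-CK threshold. The word for preference in route 1 hints at an alternative, but none is named, the same line makes CK-MB mandatory, and route 2 lacks the word.

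4. **Routes without a biomarker.** Sudden cardiac death and "Pathological findings of an acute myocardial infarction" are listed only under spontaneous MI, beyond 72 hours. Neither is offered for a peri-procedural event.

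5. **Other MI types.** The post-surgery and spontaneous definitions also name CK-MB, but they rely on tests taken around an event: within 24 hours of surgery, or a rise and/or fall. Scheduled draws in Table 1 would not supply these whichever enzyme was listed, and neither definition asks for a normal baseline CK-MB. They add nothing to this point.

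6. **Reach.** MI is not a component of the hierarchical primary endpoint (5.1.1), the powered secondary endpoints including MAE (5.1.2 and Appendix II), the descriptive endpoints (5.1.3) or the Single-arm endpoints (5.2). What remains is the adverse-event record. SAP section 3.2 shows no category for events that could not be evaluated, so an unclassifiable case could remain in the denominator as a subject without an event.

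**The case against.** The strongest reply is that little depends on this. MI enters no endpoint. Protocol section 4 gives cause of death, HF hospitalization and MAE components as examples of what the CEC adjudicates and does not name MI. The CEC charter, which is not among the documents, may list MI or say how such cases are handled. Suspected events are still captured, because any untoward medical occurrence, including an abnormal laboratory finding, is an adverse event (8.1.1), and all adverse event data go to the sponsor (8.3.1). Table 1 sets the minimum tests and does not bar an unscheduled CK-MB when MI is suspected.

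Most of this stands, and it limits the point to one event type outside every endpoint. It does not remove the point. Reporting an adverse event is not the same as classifying it under the Protocol's definition, and an unscheduled test cannot restore a baseline CK-MB that was never measured.

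A reader might go further and infer that the MI rate in device recipients will be too low by a calculable fraction, namely the share of sites running CK only. The documents do not support this. They do not give that share or show that any site runs CK only. The inference also needs equal MI risk across sites, every peri-procedural MI at a CK-only site being missed, and no unscheduled CK-MB. Nor do they support reading the gap as a failure of MI classification in general, since the post-surgery and spontaneous definitions do not depend on Table 1.

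**Conclusion.** The mismatch is real and holds for peri-procedural MI only. A site that draws total CK complies with Table 1 yet cannot supply the baseline CK-MB that both routes require. Peri-procedural MI may therefore be under-ascertained among procedure recipients, differently by site.

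The size is unknown, and no estimate is offered. The practical effect assumes that at least some sites run CK only and that MI is among the events the CEC adjudicates; the documents confirm neither. No powered test and no prespecified endpoint changes, so the 30-day MAE comparison with its performance goal is untouched. The point merits correction because the change is cheap and bears on the safety record.

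**What to change.** Reconcile Table 1 with the peri-procedural MI definition in Appendix II:

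- In the Table 1 chemistry row, require CK-MB, with CK optional, at baseline and at the existing post-procedure or discharge draw. Where screening bloods stand in for baseline, the same should apply to them.
- Apply this to Device, Single-arm and Roll-in subjects, and to Control subjects who cross over. The heading of section 7.8 does not name crossovers, and section 7.11 specifies only rescreening and a 30-day visit for them, so the text should say that the draw applies.
- Note that the post-procedure draw should fall within the definition's 72-hour window. This is an added timing constraint, because section 7.8 sets no such limit.
- In SAP section 3.2, state that wherever adjudicated MI is tabulated, subjects with CK only are listed as not evaluable for peri-procedural MI by the enzymatic criterion.

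If the sponsor prefers to keep CK as an accepted test, the alternative is for Appendix II to state how a peri-procedural MI is classified when only CK is available.

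The cost is a minor assay charge at sites that now run CK only, one table edit with a timing note, and one SAP sentence. For subjects already treated, no new data are needed.
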